## 2.4 Blinding

The study vaccines were administered in an observer-blind fashion.

In order to maintain an observer-blind design, investigators, site staff, participants, and CRO staff with oversight of study conduct remained blinded to vaccine assignments for the study duration. The Sponsor and Arcturus' representatives with direct safety oversight of the study remained blinded to individual participant vaccine assignments until the time that the study is fully unblinded. The Switchover/Further Study Vaccine occurred in a blinded fashion and participants and blinded site and Sponsor personnel remained blinded to treatment assignment until End of Study (EOS).

Additional members of the Sponsor team that were not involved in direct oversight of the study may have received unblinded study data but did not share any unblinded information with the Sponsor team overseeing the study. Sponsor staff and other persons that became unblinded at the various data analysis time points were specified in a written unblinding plan prior to unblinding occurring.

Specific considerations for sponsor personnel unblinding at the time of SAP writing are described in Section 2.5 on interim analyses (IA).

A small team of individuals at Arcturus involved in the authorship of the 6-month and final SAPs was included in the list of individuals who had access to the unblinded data at the participant level through Ministry of Health (MOH) analyses (2 analyses). The first analysis was performed on the safety and immunogenicity data from participants in the Phase 1/2/3a study. The second analysis was performed on the safety, immunogenicity, and efficacy data from participants in the Phase 1/2/3a/3b portions of the study.

This was not thought to influence the development of the 6-month and final SAP which is largely streamlining the original analyses and stating specifics for the final analysis of data (more details described on Section 2.5).

No analysis of Phase 3c data was performed in the IAs, and this study part is blinded in this final analysis SAP development.

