Since not all associated data were fully cleaned, these analyses are still considered as interim. However no multiplicity adjustments will be made for these and subsequent final analyses, as the final analyses are reflective of the MOH and 6-month analyses using the same set of endpoint data.

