#### Sample Size for Phase 3b

The primary safety endpoints will be evaluated in the Phase 3b SAS and the Phase 3b RAS. With a sample size of ~16,000 participants randomized and with approximately 8,000 participants randomized in the study to receive ARCT-154 for the primary safety analysis, if the incidence rate of an adverse event is 0.1%, the probability to detect one event in 8,000 vaccinated participants is >99.9%, based upon the following formula:

$$p = 1 - (1 - R)^N$$

where R = incidence rate and N = sample size

For the overall primary efficacy objective of the study, the null hypothesis is that the vaccine efficacy (VE) of ARCT-154 to prevent first occurrence of polymerase chain reaction (PCR)-confirmed COVID-19 is  $\leq 30\%$  (ie,  $H_0^{\text{efficacy}}$ : VE  $\leq 0.3$ ).

The primary efficacy objective will be met if the lower limit of the 95% CI for VE exceeds 30%.

VE is defined as the percent reduction in the hazard of the primary endpoint (ARCT-154 versus placebo). Equivalently, the null hypothesis is as follows:

- $H_0^{\text{efficacy}}$ : HR > 0.7 (equivalently, proportional hazards VE  $\leq 0.3$ )

A Cox proportional hazard model will be used to assess the magnitude of the study group difference (ie, HR) between ARCT-154 and placebo at a 1-sided 0.025 significance level.

Under the assumption of proportional hazards over time and with 1:1 randomization of ARCT-154 and placebo, a total of 372 COVID-19 cases will provide approximately 90% power to detect a 50% reduction in hazard rate (50% VE), rejecting the null hypothesis with a 1-sided false positive error rate of 0.025.

The study will be considered positive at the primary analysis if the one-sided p-value for rejecting HR  $\geq 0.7$  is less than or equal to 0.025.

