### Phase 3b Statistical Hypothesis

The overall primary endpoints for the study are evaluated in the Phase 3b population as follows:

- The overall primary efficacy endpoint for the study is vaccine efficacy as evaluated in the Phase 3b Modified Intent to Treat (mITT) population
- The overall primary safety endpoints are those evaluated in the Phase 3b Safety Analysis Set (SAS) and Phase 3b Reactogenicity Analysis Set (RAS)

There is no hypothesis testing for safety data analysis. Where statistical methods are applied, the emphasis will be on estimation with 95% CIs.

The primary statistical analyses for VE will be performed using virologically confirmed COVID-19 cases as adjudicated in a blinded fashion by the Independent Adjudication Committee.

The null hypothesis ( $H_0^{\text{Efficacy}}$ ) as follows:  $H_0^{\text{Efficacy}}: \text{VE} \leq 30\%$

VE is estimated as 1-HR, where HR is the hazard ratio, and will be presented together with 95% CIs. The primary efficacy objective will be met if the lower limit of the 95% CI for VE exceeds 30% in the Phase 3b mITT population.

Under the assumptions of proportional hazards over time and a 50% reduction in hazard rate (50% VE) and with 1:1 randomization of ARCT-154 and placebo, a total of 372 confirmed COVID-19 cases will provide approximately 90% power to reject the null hypothesis ( $H_0: \text{VE} \leq 30\%$ ), using a log-rank test statistic with a 1-sided false positive error rate of 0.025.

The secondary efficacy objectives (and second primary objective for regulatory filings outside of Vietnam) will be met if the lower limit of the 95% CI for VE exceeds 0%.

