#### **6.2.4 Multiple Comparisons/Multiplicity**

The overall primary efficacy objective for the study is determination of VE as evaluated in the Phase 3b mITT population. Hence the study will be regarded to have met the primary objective if the null hypothesis is rejected. Hence the primary efficacy objective will be met, and the study overall declared to be positive, if the lower limit of the 95% confidence interval (CI) for VE exceeds 30%. VE is defined as the percent reduction in the hazard of the primary endpoint (ARCT-154 versus placebo).

The overall key secondary objectives for the study are Phase 3b Secondary Endpoints 1 and 2. These endpoints will be evaluated in a hierarchical fashion such that Secondary Endpoint 1 will only be evaluated in a hypothesis testing fashion if the overall primary objective of the study has been met and Secondary Endpoint 2 will only be evaluated in a hypothesis testing fashion if the null hypothesis for Secondary Endpoint 1 has been rejected.

Phase 3b secondary endpoints 3 and 4 will be evaluated in a hypothesis generating fashion with any statistical significance being nominal.

For the pooled analyses, endpoints are nominally declared as primary/secondary/exploratory, but all endpoints are evaluated as sensitivity analyses to the equivalent endpoints being assessed in the Phase 3b populations.

Phase 1/2/3a and subgroups thereof constitute a distinct substudy with its own distinct objectives and endpoints. There is no testing procedure for controlling type 1 error for Phase 1/2/3a substudy primary or secondary endpoints. As this is a substudy, and there is no evaluation of

efficacy for this substudy, no adjustment of type 1 error is applied to the overall efficacy primary endpoint.

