#### 6.4.1 Primary Efficacy Analysis

The analysis of the first primary endpoint will consider the first occurrence of confirmed, protocol-defined COVID-19 with onset between Day 36 and Day 92 inclusive.

Time at risk = [Last date at risk – (Date received 2nd dose + 7 days)]+1; where the last date at risk will be defined as COVID-19-event date or censor date, whichever comes first.

Summaries of vaccine efficacy will display the number of participants included in the analysis, number of protocol-defined COVID-19 cases (Protocol Appendix 2) and surveillance time in person-year will be summarized in each vaccine group. Surveillance time refers to the total person-time at risk (years) for the given endpoint.

The vaccine efficacy (VE) is defined as the percent reduction in the hazard rate of the COVID-19 events (ARCT-154 versus placebo). The vaccine efficacy is calculated as:

$$VE = 1 - \frac{h_{ARCT-154}}{h_{placebo}} = 1 - HR$$

where  $h_{ARCT-154}$  and  $h_{placebo}$  are hazard rates of the confirmed, protocol-defined COVID-19/Severe COVID-19/death among those in ARCT-154 group and placebo group, respectively.

Vaccine efficacy will be displayed together with 95% confidence interval (CI). Vaccine efficacy is calculated from 1-hazard ratio, where, the hazard ratio (HR) and 95% CI are measured by adjusted Cox proportional hazard regression, with the assumptions of proportional hazards over time. The p-value will be calculated from Cox proportional hazard regression.

Efficacy summaries will also include the proportion of participants with COVID-19 cases in each vaccine group will be displayed together with the Clopper-Pearson 95% CI and a comparison between ARCT-154 and Placebo with 95% CIs. A Log-Rank test p-value will be calculated (in addition to VE% Cox model p-value).

Factors to be used as covariates in Cox proportional hazard regression include:

- Risk group: A randomization stratification factor for age and health risk for severe disease;  $\geq 18$  to  $< 60$  years and “healthy”,  $\geq 18$  and  $< 60$  years and “at risk” and  $\geq 60$  years. Age and health risk at randomization collected in the CRF will be used.
- Study site region: Study site is a randomization stratification factor. However, the sites are grouped into study site region for adjustment factor. Site collected in the CRF will be used.
  - Risk group or study site region will be removed from the model when performing subgroup analysis on that variable.

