##### 6.4.2.1 Severe COVID-19

The first occurrence of confirmed, protocol-defined severe COVID-19 with onset between Day 36 and Day 92 inclusive. This endpoint includes confirmed, protocol-defined severe COVID-19

and death due to confirmed, protocol-defined COVID-19, as confirmed by the blinded Independent Adjudication Committee and adjudicated for severity.

Time at risk = [Last date at risk – (Date received 2nd dose + 7 days)]+1; where the last date at risk will be defined as COVID-19-event date or censor date, whichever comes first.

The analysis will follow the same methods as for the first primary endpoint.

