## 9.5 Example SAS code

### Time to Event/Hazard Ratio used for VE%:

```
proc phreg data=;
  class Treatment(ref='Placebo') Risk_group site_region;
  model aval*cnsr(1) = Treatment Risk_group site_region;
  estimate 'HR' Treatment 1 /exp cl;
  ods output estimates=est;
run;
```

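### Severe COVID-19 (key secondary 1) is decided by a Cox Wald interval with no zero-event rule, so 1 v 10 cases would pass while 0 v 10 would fail and close the gate to key secondary 2

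*SAP*

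**What the plan says.** - **Success rule.** SAP 6.2.3 (Phase 3b) applies one criterion to the secondary efficacy objectives and, in a parenthesis, to a second primary objective "for regulatory filings outside of Vietnam) will be met if the lower limit of the 95% CI for VE exceeds 0" percent.
- **Source of the interval.** SAP 6.4.1 defines VE as 1 minus the hazard ratio and states that "the hazard ratio (HR) and 95% CI are measured by adjusted Cox proportional hazard regression". The covariates are risk group and site region.
- **Severe COVID-19.** SAP 6.4.2.1: "The analysis will follow the same methods as for the first primary endpoint".
- **Code.** The only program given (SAP 9.5) is PHREG with the line "estimate 'HR' Treatment 1 /exp cl". That returns the estimate plus or minus 1.96 standard errors on the log scale, exponentiated: a Wald interval.
- **Gate.** SAP 6.2.4: "Secondary Endpoint 2 will only be evaluated in a hypothesis testing fashion if the null hypothesis for Secondary Endpoint 1 has been rejected".
- **Other outputs.** SAP 6.4.1 also plans a log-rank p-value and Clopper-Pearson limits for the proportion of cases in each arm. The success rule uses neither.

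The efficacy methods (6.4), missing-data section (6.2.6), change tables (Section 7) and efficacy estimand (9.2.2) contain no rule for an arm with zero events. The protocol has none either.

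**The concern.** When no ARCT-154 participant has an event, the Cox partial likelihood keeps rising as the log hazard ratio goes to minus infinity. The fit stops at an arbitrary large negative value with an enormous standard error, and the Wald upper limit for the hazard ratio is effectively infinite. The lower VE limit therefore cannot exceed 0%, however many placebo cases there are.

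The rule thus reverses at the favourable extreme: one ARCT-154 case can pass where none would fail. Severe COVID-19 is key secondary 1 and gates key secondary 2 (COVID-19 at any time after first vaccination), so a numerical artefact could remove two formal claims. SAP 7.3 records that SAP Part 2 had treated severe disease as a second primary endpoint, which shows its weight.

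The same estimation gap affects COVID-19 death (6.4.2.3), severe disease by variant (6.4.3.5) and sparse site subgroups (6.4.1.1), but none of those carries a confirmatory decision.

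**Working it through.** **The plan's own figure.** The only Phase 3b efficacy event count given is 372, for about 90% power. With HR 0.5 against a null of 0.7, one-sided 0.025 and 1:1 allocation, Schoenfeld's formula gives 4 × (1.96 + 1.2816)² / [ln(0.7/0.5)]² = 371.2, so 372; power at 372 is 90.06%. It reproduces. No event count or power is given for severe COVID-19, so every split below is an assumption, with equal person-time.

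**Formulas**, for x ARCT-154 and y placebo cases:
- Wald: upper HR = exp[ln(x/y) + 1.96 × √(1/x + 1/y)].
- Exact conditional: p_U = BetaInv(0.975, x+1, y); upper HR = p_U/(1 − p_U).
- Lower VE limit = 1 − upper HR.

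**1 v 10.** SE = √(1 + 0.1) = 1.049. Upper HR = exp(−2.303 + 2.056) = 0.781, so the Wald limit is 21.9%: pass. Exact: p_U = 0.4128, limit 29.7%: pass.

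**0 v 10.** The Wald formula has no value. Exact: p_U = 1 − 0.025^(1/10) = 0.3085, upper HR 0.446, limit 55.4%.

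**Simulated Cox fits** (8,000 per arm, three risk groups, three regions). At 1 v 10 the adjusted lower limits ran from 19.6% to 24.6%. At 0 v 10 every fit failed, adjusted or not. One convergence rule stopped at log HR −17.2 with SE about 1,720, another at −25.4 with SE 104,979; the values reflect only the stopping rule.

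| Split | Wald lower VE limit | Exact lower VE limit |
|---|---|---|
| 1 v 8 | 0.06% | not needed |
| 1 v 10 | 21.9% | 29.7% |
| 0 v 5 | none | −9.1% |
| 0 v 6 | none | 15.1% |
| 0 v 10 | none | 55.4% |
| 0 v 20 | none | 79.7% |

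For totals up to 60, the two rules always agree at 1 or 2 ARCT-154 cases. At some splits with 3 or more (3 v 11, for example) the exact rule is the stricter.

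**How often it would bite.** Given N cases, the chance that all fall on placebo is [1/(2 − VE)]^N. The chance of success sums Binomial(N, (1 − VE)/(2 − VE)) over the splits that meet each rule.

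| True VE | P(zero), N = 10 | P(zero), N = 20 | Planned rule met, N = 20 | Exact rule met, N = 20 |
|---|---|---|---|---|
| 50% | 1.7% | 0.03% | 30% | 30% |
| 80% | 16% | 2.6% | 87% | 90% |
| 90% | 39% | 15% | 84% | 99% |
| 95% | 61% | 38% | 62% | 100% |

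**Two smaller points from the same program.**
1. SAP 6.1 calls the study "considered positive at the primary analysis if the one-sided p-value for rejecting HR" ≥ 0.7 is at most 0.025, but the Cox and log-rank p-values test HR = 1. Take 372 cases and an observed VE of 43%: SE is 0.108, the lower limit 29.6% and the one-sided p against 0.7 is 0.028, so both correct tests miss. The printed two-sided p against HR = 1 is 2 × 10⁻⁷.
2. The Pooled model combines 3:1 and 1:1 cohorts with no phase term. Without covariates, HR = 0.5 × [(8000 + 750r)/8750] / [(8000 + 250r)/8250], where r is the incidence ratio of Phase 1/2/3a to Phase 3b. A true VE of 50% appears as 52.9% at r = 0 and 47.3% at r = 2 (r is assumed). Region is only a partial proxy: in the SAP 6.2.5 site table, North HMU and South PasteurHCM each hold both 1/2/3a and 3b sites.

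**The case against.** - **Wald is inferred.** Neither document uses the word, and the code is headed as an example. That is true, but no alternative is named, and the choice matters: a profile-likelihood limit, 2 − exp(1.92/n) at 0 v n, already exceeds 0% at 0 v 3.
- **The log-rank test is available.** At 0 v 10 its two-sided p is 0.0016, and the gate wording speaks only of rejecting a null hypothesis. But SAP 6.2.3 makes the interval the criterion, so turning to the log-rank test would be an unplanned choice made with the data in hand.
- **The counts and high VE values are assumed.** This stands. The only VE assumed in the plan is 50%, for the primary endpoint; at that value the two rules are practically equal. The severe definition in protocol Appendix 2 is also broad, so zero cases may be unlikely.
- **It is late.** This stands as a caution. SAP 2.4 lists some SAP authors among "individuals who had access to the unblinded data at the participant level", and SAP 2.5 says "the final analyses are reflective of the MOH and 6-month analyses using the same set of endpoint data". SAP Part 2 is not available here, so a rule there cannot be excluded, though SAP 7.2 and 7.3 list none.
- **The smaller points change no decision.** Correct: the first is labelling and the second concerns a nominal sensitivity analysis.

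**Conclusion.** The concern holds. As written, the criterion for key secondary 1 cannot be met when ARCT-154 has no severe cases, and the formal test of key secondary 2 falls with it. The chance of success therefore drops from 87% to 62% as true VE rises from 80% to 95%, given 20 severe cases. These figures assume equal person-time and severe-case totals that the documents do not supply; if ARCT-154 has at least one severe case, the gap has no effect on this endpoint. The failure at zero does not depend on the placebo count or on covariate adjustment, but it does rest on reading the example code as the planned method. The Phase 3b primary decision, which uses the interval limit against 30%, is valid and unaffected.

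**What to change.** **Main change.** Add to SAP 6.4.1 and 6.4.2: if either arm has zero events, the VE interval and the decision come from the exact conditional interval (Clopper-Pearson on the case split, converted using each arm's surveillance time), and the Cox estimate is reported as not estimable. Do not use a profile-likelihood limit for the decision: it gives 10%, 38% and 53% at 0 v 3, 4 and 5, where the exact one-sided p is 0.125, 0.063 and 0.031.

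Record the rule in SAP 7.1 as made after the unblinded Phase 3b efficacy analysis, and show the result under the existing rule beside it.

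**Smaller changes.** State that the interval governs the primary decision, or report a p-value from z = (log HR − ln 0.7)/SE, leaving the two-sided 95% interval as it is. Add a phase stratum (1/2/3a v 3b) to the Pooled Cox model.

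**Cost.** A few lines of text and one extra calculation; Clopper-Pearson is already in the SAP for proportions. The exact interval is slightly conservative and not adjusted for risk group or region. The main cost is changing a key-secondary rule after unblinding; limiting it to zero events confines the change to cases where the planned method yields no interval.

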### **Phase 3c Substudy Statistical Hypotheses**

There is no hypothesis testing for primary Phase 3c safety objective.

#### **6.2.4 Multiple Comparisons/Multiplicity**

The overall primary efficacy objective for the study is determination of VE as evaluated in the Phase 3b mITT population. Hence the study will be regarded to have met the primary objective if the null hypothesis is rejected. Hence the primary efficacy objective will be met, and the study overall declared to be positive, if the lower limit of the 95% confidence interval (CI) for VE exceeds 30%. VE is defined as the percent reduction in the hazard of the primary endpoint (ARCT-154 versus placebo).

The overall key secondary objectives for the study are Phase 3b Secondary Endpoints 1 and 2. These endpoints will be evaluated in a hierarchical fashion such that Secondary Endpoint 1 will only be evaluated in a hypothesis testing fashion if the overall primary objective of the study has been met and Secondary Endpoint 2 will only be evaluated in a hypothesis testing fashion if the null hypothesis for Secondary Endpoint 1 has been rejected.

Phase 3b secondary endpoints 3 and 4 will be evaluated in a hypothesis generating fashion with any statistical significance being nominal.

For the pooled analyses, endpoints are nominally declared as primary/secondary/exploratory, but all endpoints are evaluated as sensitivity analyses to the equivalent endpoints being assessed in the Phase 3b populations.

Phase 1/2/3a and subgroups thereof constitute a distinct substudy with its own distinct objectives and endpoints. There is no testing procedure for controlling type 1 error for Phase 1/2/3a substudy primary or secondary endpoints. As this is a substudy, and there is no evaluation of

efficacy for this substudy, no adjustment of type 1 error is applied to the overall efficacy primary endpoint.

### 6.2.5 Subgroups

The following subgroups will be assessed for some analyses as presented below:

- Age group ( $\geq 18$  to  $< 60$  years,  $\geq 60$  years) (based on data collected in CRF)
- Risk group ( $\geq 18$  to  $< 60$  years and “Healthy”,  $\geq 18$  to  $< 60$  years and “At risk”,  $\geq 60$  years) (based on data collected in CRF)
- Sex (Male, Female)
- Region (North HMU, North VMMU, South PasteurHCM)
- SARS-CoV2 variants: Delta, Omicron, Not determined (refer to section 6.4.3.4)
- Study site

Site No.	Site ID*	Site Name	Region
1	101, 201	HMU	North HMU
2	202, 302, 402	PMC Yen Phong	North HMU
3	203, 303, 403, 503	PMC Vinh Long	South PasteurHCM
4	404, 504	PMC Long Ho	South PasteurHCM
5	405, 505	PMC Cai Be	South PasteurHCM
6	406, 506	PMC Cho Gao	South PasteurHCM
7	407, 507	PMC Cao Lanh	South PasteurHCM
8	408, 508	PMC Lap Vo	South PasteurHCM
9	409	PMC Van Lam	North VMMU
10	410	PMC Van Giang	North VMMU
11	411	PMC Phu Cu	North VMMU
12	412	PMC Tien Lu	North VMMU
13	413	PMC Kim Dong	North VMMU

Site No.	Site ID*	Site Name	Region
14	414	PMC An Thi	North VMMU
15	415	PMC Khoai Chau	North VMMU
16	416	PMC Hung Yen	North VMMU
17	517	PMC Quang Xuong	North VMMU

\*The first digit of the site ID refers to phases of the study: 1=Phase 1, 2=Phase 2, 3=Phase 3a, 4=Phase 3b, and 5=Phase 3c

Selected disposition, demography, exposure, reactogenicity (refer to section 6.6.1.1 for further details), unsolicited AEs (refer to section 6.6.1.2 for further details) and SAEs outputs (refer to section 6.6.1.3 for further details) will be produced by age group, risk group, sex and study site subgroups.

Primary and secondary efficacy endpoints will be assessed by risk group, sex, region and study site subgroups. Please refer to Section 6.4.1.1.

Selected Immunogenicity analyses will be produced by age group, risk group and sex (refer to section 6.5.6 for further details)

## 6.2.6 Missing, Unused, and Spurious Data

Missing data will not be imputed and will be analyzed as if they were missing completely at random unless otherwise specified. Missing demographic data will be presented as missing and will not be included in the denominator for calculation of proportion. Methods to handle missing data for specific analysis will be described in safety, efficacy and immunogenicity sections.

For handling of missing and partial AE dates and medication dates, please refer to Section 6.6.1 and Section 6.3.3, respectively.

